15.5 Source Documentation

All data relating to study procedures will be entered by trained site personnel into the electronic case report form (eCRF) around the time of study assessment collection. The eCRF exists within an EDC system with controlled access managed by the sponsor or its designee for this study. Study personnel will be appropriately trained in the use of eCRFs before the start of the study and prior to being given access to the EDC system. Original data and any changes to data will be recorded using the EDC system, with all changes tracked by the system and recorded in an electronic audit trail.

All eCRFs should be completed by designated, trained examining personnel, or the study coordinator as appropriate.

The investigator will attest that the information contained in the eCRFs is true by providing electronic signature within the EDC system prior to database lock. After database lock, the investigator will receive a copy of the participant data for archiving at the site. At all times, the investigator has final responsibility for the accuracy and authenticity of all clinical data.

The CRAs will perform ongoing site visits to confirm that critical protocol data (i.e., source data) entered into the eCRFs by authorized site personnel are accurate, complete, and verifiable from source documents.

Source documents are where participant data are recorded and documented for the first time. They include, but are not limited to, hospital records, clinical and office charts, memoranda, evaluation checklists, recorded data from automated instruments, copies of transcriptions that are certified after verification as being accurate and complete, photographic negatives, magnetic media, and medico-technical departments involved in the clinical trial.

To facilitate monitoring, the investigator(s) and institution(s) must provide the sponsor direct access to applicable source documents and reports for trial-related monitoring, sponsor audits and IRB/IEC review. The site must also allow inspection by applicable regulatory authorities.

When clinical observations are entered directly into the site's computerized medical record system (i.e., in lieu of original hardcopy records), the electronic record can serve as the source document if the system has been validated in accordance with FDA requirements pertaining to computerized systems used in clinical research. An acceptable computerized data collection system (for clinical research purposes) would be one that (1) allows data entry only by authorized individuals, (2) prevents the deletion or alteration of previously entered data and provides an audit trail for such data changes (e.g., modifications of file), (3) protects the database from tampering and (4) ensures data preservation.

If a site's computerized medical record system is not adequately validated for the purposes of clinical research (as opposed to general clinical practice), applicable hardcopy source documents must be maintained to ensure that critical protocol data entered into the eCRFs can be verified.

15.6 Study Files and Record Retention

The US FDA regulations (21 CFR §312.62[c]) and ICH Guideline for GCP (see Section 4.9 of the guideline) require that records and documents pertaining to the conduct of this study, including eCRFs and ICFs, must be retained by the principal investigator for 2 years after the last marketing application approval in an ICH region or after at least 2 years have elapsed since formal discontinuation of clinical development of the investigational product. All state and local laws for retention of records also apply.

No records should be disposed of without the written approval of the sponsor. Written notification should be provided to the sponsor for transfer of any records to another party or moving them to another location.

For studies conducted outside the US under a US IND/IDE, the principal investigator must comply with the record retention requirements set forth in the US FDA IND/IDE regulations and the relevant national and local health authorities.

16 AMENDMENTS

Protocol modifications, except those intended to reduce immediate risk to study participants, may only be made by the sponsor. A protocol change intended to eliminate an apparent immediate hazard to participants may be implemented immediately, provided the IRB/IEC is notified within 5 days.

Any permanent change to the protocol must be handled as a protocol amendment. The written amendment must be submitted to the IRB/IEC and the investigator must await approval before implementing the changes. The sponsor or their designee will submit protocol amendments to the appropriate regulatory authorities for approval.

If in the judgment of the IRB/IEC, the investigator, and/or the sponsor, the amendment to the protocol substantially changes the study design and/or increases the potential risk to the participants, and/or has an impact on the participants' involvement in the trial, the currently approved written ICF will require similar modification. In such cases, informed consent will be renewed for participants enrolled in the study and the new ICF signed before continued participation.

17 STUDY REPORT AND PUBLICATIONS

The sponsor or their designee is responsible for preparing and providing the appropriate regulatory authorities with clinical study reports according to the applicable regulatory requirements. The publication policy of the sponsor is discussed in the investigator's clinical research agreement.

18 STUDY DISCONTINUATION

Both the sponsor and the principal investigator reserve the right to terminate the study at the investigator's site at any time. Should this be necessary, the sponsor or a specified designee will inform the appropriate regulatory authorities of the termination of the study and the reasons for its termination, and the principal investigator will inform the IRB/IEC of the same. If the decision is made to terminate the study, the sponsor and the principal investigator will assure that adequate consideration is given to the protection of the participants' interests.

The investigator may discontinue a participant from the study if warranted. The investigator and the sponsor may also request the withdrawal of a participant because of noncompliance (e.g., missed visits), administrative reasons, or any other valid and ethical reasons.

Reasons for participant discontinuation may include, but are not limited to, the following:

- Investigator determination that it is not in the best interest of the participant to continue participation
- Intercurrent illness
- AE that is serious and unexpected
- Worsening condition
- Any other safety concerns
- If a participant withdraws or is discontinued from the study, they should return for an exit visit. The schedule of assessments for this visit is the same as that for the 6-month visit.

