3 STUDY ENDPOINTS

Primary Safety Endpoints

- Number and proportion of adverse events from day of surgery through 6 months post implantation
- Number and proportion of severe adverse events from day of surgery through 6 months post implantation
- Number and proportion of ocular adverse events from day of surgery through 6 months post implantation
- Number and proportion of non-ocular adverse events from day of surgery through 6 months post implantation

Secondary Safety Endpoints

- Number and proportion of participants with a loss in BCVA of 15 or more letters from baseline in the study eye using the Early Treatment Diabetic Retinopathy Study (ETDRS) distance chart
- Number and proportion of participants with at least 1 treatment-emergent serious adverse event (SAE)
- Detectable serum levels of CNTF at Months 1, 3 and 6 post-implantations of NT-501
- Number and proportion of participants with serum Ab or Nab to CNTF, Ab to NTC-201.6A cells and Ab to DFHR at Baseline and Months1, 3 and 6 post-implantation of NT-501

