6.2 Description of the Study Procedures

6.2.1 Study Procedures

The following examinations are to be performed at the times indicated in the schedule of study procedures, where 1 month is defined as 30 days. Additional information related to these examinations is provided in the procedure specific instructions. All ocular evaluations/procedures will be completed only in the study eye unless otherwise indicated.

- Medical evaluation, as would be standard for any surgical procedure and its associated anesthesia (the tests to be performed will be site-specific); evaluation may be performed during the screening period or on the day of surgery
- Complete ophthalmic examination including:
 - External examination of the eye and adnexa
 - Pupil responsiveness
 - Manifest refraction
 - Slit lamp biomicroscopy
 - Dilated fundus examination
 - Indirect ophthalmoscopy
 - Goldmann applanation tonometry
 - BCVA (this assessment will be performed using the ETDRS visual acuity procedure, administered by a certified technician)
 - Measurement of undilated pupil diameter
- Ophthalmic assessments including:
 - SD-OCT
 - Fluorescein angiography
 - Color fundus photography
 - o External photograph of conjunctiva over implant
- Urine or blood pregnancy test for premenopausal female participants
- Serum chemistry, hematology, and urinalysis
- Serum analyses of CNTF, Ab and Nab to CNTF, Ab to NTC-201.6A cells and Ab to DFHR

Goldmann applanation tonometry, measurement of undilated pupil diameter, slit lamp biomicroscopy, dilated fundus examination, and urine or blood pregnancy testing will be performed following standard procedures at each site.

In the event of extenuating circumstances whereby an in-clinic follow-up visit cannot be conducted within the designated visit window, a Safety Check-In call should be performed, and an out of window in-clinic visit should be performed as soon as possible. Following a missed or out of window visit, every effort should be made to return the participant to the original protocol-specified visit schedule.

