9.4 Adverse Event Follow-up

Until the participant reaches the final scheduled follow-up visit, any new AEs, as well as follow-up information for ongoing AEs, must be recorded. For participants who withdraw prematurely, AEs should be followed until 30 days after last study visit.

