18.1 Premature Discontinuation

Premature discontinuation is not anticipated to be a frequent event based on the history of previous clinical trials with this implant. The investigator may discontinue a participant from the study if warranted and only after discussion with the medical monitor. If the participant discontinues study participation before completing the defined 6 months of follow-up, the principal investigator and study coordinator of the study site for the NHOR will be notified to ensure long-term follow-up.

If a participant requests explanation and withdrawal from the study, this can be readily arranged. The investigator should contact the sponsor's medical monitor to discuss the reasons for the request and discuss the procedure for explanation. If a participant discontinues from the study, they will not be replaced once recruitment is complete.

If a participant requests explanation but does not wish to withdraw from the study, this is also acceptable. The participant would continue in the study with all planned follow-up visits and assessments.

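### Participants can be discontinued from the study for outcome-related reasons while still implanted, and AE follow-up then ends 30 days after the last visit instead of at Month 6

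*Protocol*

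**What the plan says.** Protocol Section 18 gives the discretion in general terms: "The investigator may discontinue a participant from the study if warranted". Its list of possible reasons includes "AE that is serious and unexpected", "Worsening condition" and other safety concerns. Separately, the investigator and the sponsor "may also request the withdrawal of a participant because of noncompliance (e.g., missed visits), administrative reasons", or for other valid and ethical reasons. A participant who leaves is expected, though not strictly required, to return for an exit visit with the same assessments as Month 6. Section 18.1 adds that the investigator must first discuss a discontinuation with the medical monitor, and that early discontinuation is not expected to be frequent.

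Treatment is one operation. Under Section 7.3 the implant stays in for the study unless there is intolerance, a complication or a participant request. Leaving the study does not by itself lead to removal.

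The first primary endpoint (Section 3) is "Number and proportion of adverse events from day of surgery through 6 months post implantation". For early leavers, Section 9.4 says: "For participants who withdraw prematurely, AEs should be followed until 30 days after last study visit". Section 10.3 follows known SAEs to resolution or stability. Section 11.3.1 evaluates early leavers on the visits they attended, and SAP 3.10 makes no substitution for missing data. Section 18.1 has the natural history registry (NHOR) notified, but Section 4.1 makes joining it the participant's choice.

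Two other passages lean towards keeping people under observation. For a participant who requests explant without wishing to withdraw, Section 18.1 says: "The participant would continue in the study with all planned follow-up visits and assessments". For missed visits, Section 6.2.1 says: "Following a missed or out of window visit, every effort should be made to return the participant to the original protocol-specified visit schedule".

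**The concern.** With a one-time implant, ending study participation need not end exposure; what it ends is data collection. Several of the listed reasons are themselves safety outcomes, so the participants whose follow-up is cut short may be those at highest risk of further events. That is informative loss in a study whose purpose is to describe safety to Month 6.

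The analysis does not compensate. SAP 4.3 uses crude subject incidence, so a participant who leaves early counts as free of anything that would have started later. The Month 3 and Month 6 BCVA rates drop that participant unless an early exit visit is placed in one of those rows, and the SAP has no rule for that. Late events are not hypothetical: Protocol 1.1 (Background) reports one case of grade 3 inflammation in the Phase 2 MacTel study first noted at 6 months.

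**Working it through.** The documents give no dropout rate and no formal sample size, so there is no plan figure to reproduce. The inputs are the 180-day window (Month 6 is Day 180 in the visit schedule), Month 1 at Day 30 and Month 3 at Day 90, the 30-day AE follow-up (Section 9.4), the minimum of 30 participants (Section 5.1) and the Clopper-Pearson interval (SAP 4.4.2).

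**1. AE window lost for one early leaver.** Section 9.4 is read generously, as covering new AEs and as applying to participants who are discontinued as well as those who withdraw. Fraction uncaptured = (180 − (last visit day + 30)) / 180.
- Last visit Day 30: (180 − 60)/180 = 120/180 = 67%.
- Last visit Day 90: (180 − 120)/180 = 60/180 = 33%.

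A later exit visit moves the last visit and shortens the gap.

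**2. Total observation lost.** Planned person-time is 30 × 180 = 5,400 days. If 1 to 3 participants (assumed) have their last visit at Day 30, the loss is 120/5,400 = 2.2% to 360/5,400 = 6.7%. In total this is small, but it falls on selected participants.

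**3. Weight of one participant.** 1/30 = 3.3 percentage points.

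**4. BCVA loss of 15 letters or more.** Assume 3 of 30 participants truly have the loss at Month 6 and k of them are discontinued earlier. If their exit visits are left out of the Month 6 row, the observed rate is (3 − k)/(30 − k):

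| k | Month 6 rate | 95% interval |
|---|---|---|
| 0 | 3/30 = 10.0% | 2.1% to 26.5% |
| 1 | 2/29 = 6.9% | 0.8% to 22.8% |
| 2 | 1/28 = 3.6% | 0.1% to 18.3% |
| 3 | 0/27 = 0% | 0% to 12.8% |

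If the exit visit is recorded as Visit 7 and already shows the loss, Month 6 stays at 3/30. SAP 3.11 tabulates by the visit recorded on the CRF and does not settle which branch applies. The any-visit figure in SAP 4.4.2 stays at 3/30 on either branch, provided the loss was measured by exit.

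**5. What is kept and what can be lost.** Kept: the triggering AE or SAE, because the Safety Population (SAP 2.1) retains everyone implanted with at least one safety measurement; the course of known SAEs; and one full assessment set, if the exit visit takes place. At risk: new AEs starting more than 30 days after the last visit; BCVA, IOP, CNTF and antibody results after exit; and a place in the Month 3 and Month 6 rates.

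**The case against.** The strongest reply is that the plan already has several safeguards: medical-monitor discussion, a full exit assessment, 30 days of AE follow-up, SAE follow-up to resolution or stability, and notice to NHOR. Discontinuation is discretionary and expected to be infrequent, and nothing is being tested. All of that stands and limits the size of the problem. It does not close the gap. Discussion with the monitor does not require continued follow-up, one early assessment cannot show later events, and neither document brings NHOR data into these endpoints.

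A reader might infer four stronger things that the documents do not support.
- **That Section 18 contradicts Sections 18.1 and 6.2.1.** The explant sentence covers a participant who does not wish to withdraw. The Safety Check-In call is for extenuating circumstances, and trying to restore the schedule can coexist with a discretionary power to withdraw. The approaches differ; the rules do not collide.
- **That the worst outcomes vanish from the safety results.** The triggering event stays in the subject incidence, and BCVA loss seen by exit stays in the any-visit figure.
- **That the sponsor may remove someone for a serious AE.** The list of reasons names no decision-maker; the sponsor is named for noncompliance, administrative and other valid reasons.
- **That 67% and 3.6% are the expected effects.** Each is one case, resting on an early last visit or on one way of tabulating the exit visit.

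**Conclusion.** The point holds in a limited form. As written, follow-up may be ended for outcome-related reasons while the implant remains in place. New AEs more than 30 days after the last visit, and all later scheduled assessments, are then outside the study's data. For AE incidence and BCVA loss the likely direction is towards apparent safety; for CNTF and antibody results the direction cannot be stated.

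The size depends on timing and number: 67% of one participant's AE window if the last visit is Day 30, 33% if it is Day 90, about 3.3 percentage points per participant, and 2.2% to 6.7% of total person-time for 1 to 3 leavers at Day 30. The numbers of leavers and of true BCVA losses are assumptions. With discontinuation expected to be infrequent and the analysis descriptive, this is a cheap improvement and not a defect that undermines the study.

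**What to change.** Leave the investigator's discretion, the listed grounds, and all implant and care decisions as they are. Deleting grounds would narrow stated safety discretion and would not work, because best-interest, administrative and other valid reasons would remain.

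In Protocol Sections 18 and 9.4, state that a participant discontinued for any reason other than withdrawal of consent is asked to stay on the planned visits to Month 6. Where in-clinic visits are not possible, the existing Safety Check-In call (Section 6.2.1) is made at each remaining visit date. AEs are recorded to Day 180 either way.

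In the SAP:
- Tabulate an early exit visit as its own visit, not as Month 6, and say that it counts towards the any-visit BCVA figure.
- Keep the table of withdrawal reasons in SAP 4.1 and add the day of last AE capture, so that outcome-related discontinuations and their follow-up time can be seen.

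The cost is a protocol wording change, two SAP sentences, and a few extra visits or calls for participants who would otherwise have left. Some may decline, so the gap is reduced and not removed.

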18.1 Premature Discontinuation

Premature discontinuation is not anticipated to be a frequent event based on the history of previous clinical trials with this implant. The investigator may discontinue a participant from the study if warranted and only after discussion with the medical monitor. If the participant discontinues study participation before completing the defined 6 months of follow-up, the principal investigator and study coordinator of the study site for the NHOR will be notified to ensure long-term follow-up.

If a participant requests explanation and withdrawal from the study, this can be readily arranged. The investigator should contact the sponsor's medical monitor to discuss the reasons for the request and discuss the procedure for explanation. If a participant discontinues from the study, they will not be replaced once recruitment is complete.

If a participant requests explanation but does not wish to withdraw from the study, this is also acceptable. The participant would continue in the study with all planned follow-up visits and assessments.

19 CONFIDENTIALITY

All information generated in this study is considered highly confidential and must not be disclosed to any person or entity not directly involved with the study unless prior written consent is gained from the sponsor. However, authorized regulatory officials, IRB/IEC personnel, and the sponsor and its authorized representatives are allowed full access to the records. The participants' names will not appear on any of the data forms reported to the CRO. Participants will be identified by a study number. The date of birth of each participant will be collected in the data system.

| CNTF | ciliary neurotrophic factor |
| CRA | clinical research associate |
| CRF | case report form |
| CRO | contract research organization |
| DHFR | dihydrofolate reductase |
| DSMC | data and safety monitoring committee |
| eCRF | electronic case report form |
| ECT | encapsulated cell therapy |
| EDC | electronic data capture |
| ETDRS | Early Treatment Diabetic Retinopathy Study |
| EZ | ellipsoid zone |
| FDA | Food and Drug Administration |
| GCP | Good Clinical Practice |
| HFM | hollow fiber membrane |
| ICF | informed consent form |
| ICH | International Conference on Harmonisation |
| IDE | investigational device exemption |
| IEC | independent ethics committee |
| IND | investigational new drug |
| IOP | intraocular pressure |
| IRB | institutional review board |
| IReST | International Reading Speed Texts |
| IS/OS | inner segment/outer segment junction line |
| MacTel | macular telangiectasia type 2 |
| MedDRA | Medical Dictionary for Regulatory Activities |
| Nab | Neutralizing antibodies |
| NEI-VFQ-25 | National Eye Institute Visual Function Questionnaire-25 |

| | |
|----------------------|---|
| NHOR | Natural History and Observation and Registry Study of Macular Telangiectasia Type 2 |
| OCT | optical coherence tomography |
| ONL | outer nuclear layer |
| PET yarn | polyethylene terephthalate yarn |
| PSNS | parasympathetic nervous system |
| RP | retinitis pigmentosa |
| RPE | retinal pigment epithelium |
| SAE | serious adverse event |
| SD-OCT | spectral-domain optical coherence tomography |
| SE | standard error |
| SOE | Schedule of events |
| SRNV | subretinal neovascularization |
| SUSAR | serious unexpected suspected adverse reaction |
| TEAEs | treatment-emergent AEs |
| US, USA | United States |
| VLDLR | very low-density lipoprotein receptor |
| Vldlr ^{-/-} | very low-density lipoprotein receptor knockout (mouse) |

1. INTRODUCTION AND OBJECTIVES

1.1. Introduction

Idiopathic macular telangiectasia type 2 (MacTel) is a bilateral neuro/vascular/glial degenerative condition of unknown etiology with characteristic neurosensory atrophy, perifoveal telangiectatic vessels, and diffuse hyperfluorescence in the late phase of fluorescein angiography. Other characteristic findings include loss of retinal transparency, crystalline deposits, a decrease or absence of macular pigment, and hyperplasia of the retinal pigment epithelium (RPE) in the macular area. Spectral-domain optical coherence tomography (SD- OCT) assessments show disruption of the photoreceptor inner segment/outer segment junction line (IS/OS line) or ellipsoid zone (EZ), and hyporeflective cavities in both the inner and outer retina.

There is significant evidence to support the use of ciliary neurotrophic factor (CNTF) as a potential therapy for retinal degenerative diseases. Histopathologic studies in naturally occurring and genetically engineered animal models of photoreceptor dysfunction and death that phenotypically model retinitis pigmentosa (RP), have indicated the promise of CNTF as an effective therapeutic agent for reducing photoreceptor loss associated with degeneration of the cells of the outer retina. CNTF is one of several neurotrophic factors that are produced endogenously by neurons or Müller cells. CNTF has been demonstrated to be effective in retarding photoreceptor neuron loss in animal models of retinal degeneration of various forms, including environmental light stress.

Although CNTF is an attractive therapeutic candidate for neurodegenerative diseases, it is significantly handicapped by its extremely short half-life. Neurotech Pharmaceuticals, Inc. has developed the NT-501 implant to treat retinal degenerative diseases. The NT- 501 implants are positioned into the vitreous cavity with a surgical procedure that may be performed under local/monitored anesthesia care. These implants consist of a sealed semipermeable hollow fiber membrane (HFM) capsule surrounding a scaffold of 6 strands of polyethylene terephthalate yarn, which have been loaded with CNTF-secreting NTC-201.6A cells. The NT- 501 implants are positioned into the vitreous cavity with a surgical procedure that may be performed under local/monitored anesthesia care. These implants consist of a sealed semipermeable hollow fiber membrane (HFM) capsule surrounding a scaffold of 6 strands of polyethylene terephthalate yarn, which have been loaded with CNTF-secreting NTC-201.6A cells.

